6. ACCRUAL AND ANALYSIS

6.1. Sample size

The sample size for the primary outcome of this trial has been chosen to give good statistical power to preclude any clinically important inferiority of vNOTES compared to laparoscopy and is based on evidence retrieved from a systematic review of the literature (15) and a RCT comparing the excision of mature teratoma using culdotomy with and without laparoscopy (17). An important consideration in adnexal mass surgery is the inadvertent opening of the ovarian capsule. The likelihood of cyst rupture during removal by laparotomy or laparoscopy ranges from 10.5% to 41.8% in published studies (15). Based on a low failure rate to remove dermoid cysts by colpotomy using laparoscopy (2.4%), according to the findings from a RCT (17) we assumed a successful removal of adnexal cysts without spill to be feasible in 95% of all cases. We calculated the sample size with a one-sided test for non-inferiority studies for the primary outcome. The vNOTES approach may be more convenient for women in that no scar in the abdominal wall is required. We believe, therefore, that vNOTES would be the treatment of choice even if 15% less women had successful removal of a benign adnexal mass by using the vNOTES approach. Non inferiority will be concluded when 15% lies above the upper limit of the 95% confidence interval calculated for the difference in the proportion of women successfully treated with either of both techniques. To achieve 80% power to demonstrate non-inferiority under the assumption of similar success rates of 95% in both groups a sample size of 54 participants (27 women per group) will be required. The target sample size was increased to 64 participants (32 women per group) to account for a drop-out rate of 15%.

(<https://www.sealedenvelope.com/power/binary-noninferior/>). Based on the power calculations for the primary outcome, the use of three strata for the randomisation and assuming a loss-to-follow-up rate of 15 % we decided to include 66 study participants in the NOTABLE trial.

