6.3. Statistical Analysis

We will calculate a 95% confidence interval of the difference in the proportions of women with a successful removal of an adnexal cyst. Non inferiority of the intervention (vNOTES) will be concluded

when 15% lies above the upper limit of this confidence interval. For this primary analysis, adjustments for prognostic factors will not be made in the first instance; the effect of the variables listed in Section 3.5 (Stratification of randomisation) will be explored as a secondary analysis. Continuous measures (VAS scores) will be analysed using analysis of covariance (adjusting for baseline value). Multilevel models for repeated measurements will also be used to compare the mean differences in VAS pain scores between groups overall at all time points, thereby maximising the power of the data available.

Analysis will be performed on an 'intention to treat' basis in the first instance as recommended in the CONSORT statement. A 'per protocol' analysis will also be performed to test the robustness of the results obtained. As a conservative measure, estimates of effect sizes between the two arms will be presented as point estimates with two-sided 95% confidence intervals. The trial can only conclude non-inferiority if 15% lies out of the upper band of the confidence interval (i.e. vNOTES 15% less successful than laparoscopic treatment).

Baseline characteristics of the patients enrolled in the two groups will be compared to ensure that randomisation has produced comparable groups of participants, and will be covariates in the modelling procedure.

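### The 80% power stated for 54 women is a normal-approximation figure at 1.35 expected failures per arm; by exact calculation at one-sided 5%, Newcombe or score-type intervals give about 62% at 54 women and about 76% at 66

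*Protocol*

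**What the plan says.** Section 6.1 (Sample size) bases the trial on a one-sided calculation: "We calculated the sample size with a one-sided test for non-inferiority studies for the primary outcome". The margin is 15 percentage points, since vNOTES would be preferred "even if 15% less women had successful removal of a benign adnexal mass by using the vNOTES approach". The power statement reads "To achieve 80% power to demonstrate non-inferiority under the assumption of similar success rates of 95% in both groups", and the answer given is 54 women, 27 per group, from an online calculator. Enrolment is then raised to 64 for 15% drop-out and set finally at 66.

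The decision rule in 6.1 is "Non inferiority will be concluded when 15% lies above the upper limit of the 95% confidence interval" for the difference in success proportions. Section 6.3 (Statistical Analysis) repeats it: "We will calculate a 95% confidence interval of the difference in the proportions of women with a successful removal of an adnexal cyst". It adds that "estimates of effect sizes between the two arms will be presented as point estimates with two-sided 95% confidence intervals". Neither section names the type of interval or gives alpha as a number. Section 5.1.2 has the primary outcome measured at the end of surgery.

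**The concern.** With 95% success and 27 women per arm, the whole primary comparison is expected to contain about three failures. A normal approximation to a difference of proportions is unreliable there. The plain interval is too short: with no failures in either arm its width is zero. It therefore declares non-inferiority too often when vNOTES is truly 15 points worse. An interval that corrects this passes fewer tables, and power falls.

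Two things are at stake. The stated power may belong only to a rule that exceeds its own error rate. And because the result turns on one or two failures, the choice of interval can decide the conclusion.

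**Working it through.** **Inputs** (section 6.1 unless noted). Failure rate 5% in both arms; margin 0.15; 80% power; one-sided test; 27 per group; 66 enrolled. Alpha is not stated and is inferred in step 1. The two-sided 95% interval is from section 6.3.

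**1. Reproduce the 27.** Unpooled normal approximation: n = (z_alpha + z_power)² × 2 × 0.95 × 0.05 / 0.15².
- One-sided 5%: (1.645 + 0.842)² × 0.095 / 0.0225 = 26.1, rounded up to 27.
- One-sided 2.5%: 34.

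So the sizing used one-sided 5%. For drop-out, 54 / 0.85 = 63.5, giving 64. The arithmetic is sound.

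**2. Expected failures.** 27 × 0.05 = 1.35 per arm.

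**3. Exact enumeration, 27 per arm, one-sided 5%.** All 28 × 28 outcome tables are taken, each interval's rule (upper limit below 15%) is applied, and binomial probabilities are summed. Power is at 5% v 5% failures. Error is at 5% (laparoscopy) v 20% (vNOTES).

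| Interval | Power | Error at 5% v 20% | Largest error over control failure rates |
|---|---|---|---|
| Plain (Wald) | 80.5% | 7.7% | 8.6% (control 2%) |
| Hauck-Anderson | 70.7% | 4.5% | 7.2% (control near 0) |
| Newcombe, Farrington-Manning, Miettinen-Nurminen | 61.8% | 4.2% | 6.4% (control near 42%) |

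The exact unconditional test also has 61.8% power and stays at or below 5% throughout. The largest power of any non-randomised rule with error at or below 5% at every control rate is 62.5%.

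**4. Where the power goes.** With 0, 1, 2 or 3 laparoscopy failures, Wald tolerates up to 1, 2, 2 or 3 vNOTES failures; Newcombe and score tolerate 0, 1, 2 or 2. The tables lost (laparoscopy v vNOTES failures) are 0 v 1, 1 v 2 and 3 v 3. With binomial probabilities 0.2503, 0.3558, 0.2434 and 0.1068 for 0 to 3 failures in 27 at 5%:
- 0.2503 × 0.3558 = 0.089
- 0.3558 × 0.2434 = 0.087
- 0.1068² = 0.011

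The sum is 0.187, which is the gap 80.5% − 61.8%.

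**5. The planned 66 women, all evaluable (33 per arm).**

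| Interval | One-sided 5%: power / error at 5% v 20% | Two-sided 95% limit: power / error at 5% v 20% |
|---|---|---|
| Plain (Wald) | 85.1% / 6.5% | 80.7% / 4.2% (nominal 2.5%) |
| Hauck-Anderson | 81.1% / 4.8% | 73.5% / 2.8% |
| Newcombe | 76.2% / 4.7% | 59.2% / 2.2% |
| Farrington-Manning, Miettinen-Nurminen | 76.1% / 4.4% | 59.2% / 2.2% |

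**6. Example.** With 2/33 vNOTES failures against 0/33 and a two-sided 95% interval, the upper limit is 14.2% by Wald (non-inferior) and 19.6% by Newcombe (not shown).

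**The case against.** **The interval belongs in a statistical analysis plan.** This is fair. Such a plan may exist, and an unnamed interval would not by itself be a finding. A reader might infer that the protocol adopts the plain interval for its analysis; it does not say so. What stands is the power sentence in 6.1. None of the error-controlling intervals tested restores 80% at 54 women.

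**Power is not 62% for every interval that controls error.** A reader might infer that it is. If error is checked only at 5% v 20% failures, Hauck-Anderson passes with 70.7% power. The ceiling of 62.5% applies only if error must stay at or below 5% at every control rate, and the Newcombe and score intervals recommended here do not meet that test strictly either (6.4% near a 42% control failure rate). Even so, 70.7% is short of 80%.

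**The trial enrols 66, not 54.** This also stands. The primary outcome is measured at the end of surgery, so few losses are likely. At one-sided 5% the shortfall with Newcombe or score intervals is then about 4 points. Hauck-Anderson reaches 81.1%, but its error rises to 10.9% when control failures are near zero. Setting 62% (27 per arm, one-sided 5%) beside 59% (33 per arm, two-sided 95%) as one result would mix two alphas; part of the second gap comes from the stricter limit.

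**The figure is discrete.** At 27 per arm, one vNOTES failure against none misses by a hair under Newcombe (upper limit 15.01%). At 28 per arm Newcombe power is 71.0%. It first reaches 80% at 38 per arm.

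**Failures may be commoner than 5%.** Section 6.1 cites rupture rates of 10.5% to 41.8%. Over that range of control failure rates the plain interval's error with 27 per arm is about 5.3% to 6.4%, so the inflation is modest. But the 80% is stated at 95% success and has to be judged there.

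**Conclusion.** The concern holds for the power statement in section 6.1. The 80% at 54 women is obtained only with a plain interval whose error at the planning rates is 7.7% against an implied 5%. With Newcombe or score-type intervals it is 61.8%. For the 66 women planned, the comparable figure is about 76% at one-sided 5%, and about 59% if the two-sided 95% interval of section 6.3 decides.

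This is a fault of method: a reader should not infer that 27 per group was miscalculated, or that the trial as enrolled has only 62% power at one-sided 5%.

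The conclusion assumes 5% failures in both arms for power, 5% v 20% for error, one-sided 5% inferred from the 27, and no missing primary outcomes at 33 per arm.

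**What to change.** - **Section 6.3:** state that non-inferiority is decided on a score-type interval (Miettinen-Nurminen or Farrington-Manning) or a Newcombe interval, and give the alpha as a number.
- **Section 6.1:** say that the 27 per group came from a normal approximation, and replace the 80% with the exact power of the chosen interval at that alpha. At one-sided 5% this is about 62% for 27 per arm and about 76% for 33 per arm. With a two-sided 95% limit it is about 59% for 33 per arm.

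This costs about two sentences. Enrolment and margin are unchanged, and no extra women are asked for. The only downside is a less favourable stated power.

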5.1.2 Timing of assessments

The primary outcome will be measured clinically at the end of the surgical procedure. In addition PROMs will take place the evening of the surgical intervention (return home), during the first postoperative week (pain by VAS scores and medication) and at 3 and 6 months (dyspareunia and sexual wellbeing). Clinical physician assessment will take place the evening of the surgical intervention (return home) and during the first six weeks following surgery (pelvic infection, surgical complications).

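### The sample size of 54 gives 80% power at one-sided 5%, but the non-inferiority rule uses a two-sided 95% limit, under which 54 women give about 71%

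*Protocol*

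**What the plan says.** Protocol section 6.1 gives the design inputs:

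- The test: "We calculated the sample size with a one-sided test for non-inferiority studies for the primary outcome". No alpha is stated.
- The success rate: "we assumed a successful removal of adnexal cysts without spill to be feasible in 95% of all cases".
- The margin is 15 percentage points and the power 80%. The result is given "under the assumption of similar success rates of 95% in both groups a sample size of 54 participants (27 women per group").
- The 54 become 64 for 15% drop-out, and the final target is 66.

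The same section gives the decision rule: "Non inferiority will be concluded when 15% lies above the upper limit of the 95% confidence interval" for the difference in success proportions. It does not say whether that interval is one-sided or two-sided.

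Section 6.3 repeats the rule and then adds: "As a conservative measure, estimates of effect sizes between the two arms will be presented as point estimates with two-sided 95% confidence intervals". The sentence that follows reads: "The trial can only conclude non-inferiority if 15% lies out of the upper band of the confidence interval".

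On timing, section 5.1.2 says: "The primary outcome will be measured clinically at the end of the surgical procedure".

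**The concern.** The upper limit of a two-sided 95% interval leaves 2.5% in the tail that decides non-inferiority. A one-sided test at 5% leaves twice that. If the sample size was computed for one and the conclusion is drawn from the other, the 80% in section 6.1 does not belong to the test that will be done.

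Two things are at stake. First, section 6.1 treats 54 evaluable women as sufficient and everyone above 54 as cover for drop-out; under the stricter limit those women are needed to reach the stated power. Second, in a trial this small some plausible results pass one limit and fail the other. If the limit is not fixed in writing before the data are seen, it could be chosen afterwards.

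**Working it through.** **Inputs.** From section 6.1: success 95% in both arms, true difference 0, margin 0.15, power 80%, equal allocation. Alpha is not stated, so both candidates are tried. Normal quantiles: 1.645 (5%), 1.960 (2.5%), 0.842 (80% power).

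**1. Reproduce the protocol's figure.**

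n per group = (z_alpha + z_power)² × 2 × 0.95 × 0.05 / 0.15²

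- Alpha 5%: (1.645 + 0.842)² × 0.095 / 0.0225 = 26.1, so 27 per group and 54 in all. Then 54 / 0.85 = 63.5, so 64. Both match section 6.1.
- Alpha 2.5%: (1.960 + 0.842)² × 0.095 / 0.0225 = 33.1, so 34 per group and 68 in all. This does not match.

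The sample size was therefore computed at one-sided 5%.

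**2. Power under each limit.**

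Power = Φ(0.15 / √(0.095 / n) − z_alpha), with n per group. For n = 27, 0.15 / √(0.095 / 27) = 2.529:

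- One-sided 5%: Φ(2.529 − 1.645) = 81.2%.
- Two-sided 95% limit: Φ(2.529 − 1.960) = 71.5%.

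As a check, the rule was also enumerated exactly: all pairs of binomial counts at 95% versus 95%, declaring non-inferiority when the Wald upper limit for laparoscopy minus vNOTES is below 0.15. At 27 per group the one-sided 95% limit gives 80.5%. For the two-sided 95% limit:

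| Evaluable women | Normal approximation | Exact, Wald limit |
|---|---|---|
| 54 | 71.5% | 70.7% |
| 56 (66 × 0.85 = 56.1) | 73.1% | 69.7% |
| 60 (about 90% of 66) | 76.0% | 76.5% |
| 64 | 78.6% | 81.7% |
| 66 | 79.8% | 80.7% |

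Exact power does not rise smoothly with n because the outcome is discrete, so differences of a point or two between adjacent rows mean little.

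**3. A result on which the two limits disagree.** Take 26/27 successes with laparoscopy and 25/27 with vNOTES. The difference is 0.037 and its standard error is √(0.963 × 0.037 / 27 + 0.926 × 0.074 / 27) = 0.062. The upper limit is 0.037 + 1.645 × 0.062 = 0.139 one-sided (non-inferior) and 0.037 + 1.960 × 0.062 = 0.159 two-sided (not shown).

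**4. True error of the Wald rule.** Exact enumeration at the margin, 95% versus 80%:

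| Limit | 27 per group | 33 per group |
|---|---|---|
| Two-sided 95% | 4.5% | 4.2% |
| One-sided 95% | 7.7% | 6.5% |

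Both limits exceed their nominal level (2.5% and 5%), so each should be described as nominal.

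**The case against.** **The two-sided interval may be for presentation only.** Section 6.1 announces a one-sided test, the rule itself is always stated with an interval of unspecified sidedness, and two-sided appears once, about how effect estimates are presented. A one-sided 5% test reported alongside a stricter interval is coherent, and the 80% would then be right. This reading is possible but the weaker one. The sentence directly after the two-sided interval draws the non-inferiority conclusion from the confidence interval, that interval is called conservative, and no one-sided bound is mentioned anywhere. Even if it was intended, the protocol would still have to say so.

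**The practical effect is small.** This stands. The trial enrols 66, and the primary outcome is recorded in theatre. The 15% and 90% figures concern follow-up and questionnaires and should hardly touch it. Power is then close to 80% even under the stricter limit. By exact enumeration 64 evaluable women also reach 80%, so not quite every woman is needed.

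**The 2.5% would itself be only nominal.** This stands too: with a Wald interval the true error is 4.2 to 4.5%. The wording adopted should say nominal and disclose this.

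**The interval method is not named.** That can be left to a statistical analysis plan and is not a fault here. It matters only because every power figure above assumes a Wald interval.

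**Conclusion.** The concern holds. As the rule is most naturally read, the 80% attached to 54 women belongs to a one-sided 5% test and not to the two-sided 95% limit that decides the trial. At 54 evaluable women the shortfall is about 9 percentage points (71.5% by normal approximation, 70.7% exact). With the planned 15% loss, power is about 70 to 73%. With nearly all of the 66 evaluable it is about 80%, and that is the likely situation given when the outcome is measured.

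This rests on 95% success in both arms, a Wald-type interval, and an alpha of 5% inferred from its being the value that reproduces 54 and 64. If a one-sided 95% bound was meant, the power statement is correct but the decision rule lacks the word that determines the result. It should be fixed on either reading. It does not threaten the feasibility of the trial.

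**What to change.** Keep the two-sided 95% limit.

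- In sections 6.1 and 6.3, state that non-inferiority is tested at nominal one-sided alpha 2.5%, using the upper limit of the two-sided 95% interval for laparoscopy minus vNOTES.
- Restate the power in 6.1: about 71% with 54 evaluable women, about 70 to 73% with 56, and about 80% only if nearly all 66 have primary-outcome data.
- Say that these figures assume a Wald interval, whose true error at the margin is about 4.2 to 4.5%. As a caution, an interval that holds its level costs power: a Newcombe interval gives about 55% at 27 and 59% at 33 per group, with true error of 2.4% and 2.2%.

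The cost is protocol wording, a less favourable power statement for 54 women, and an explicit dependence on near-complete primary-outcome data. No extra enrolment is required. A sponsor who wants 80% power after the planned loss would need 68 evaluable women, or 68 / 0.85 = 80 enrolled.

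If a one-sided 95% bound was intended, both sections must say so and acknowledge a nominal 5% error, with a true Wald error of about 7.7% at 27 and 6.5% at 33 per group. That would relax a limit the protocol calls conservative.

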6.2. Projected accrual and attrition rates

It is anticipated that recruitment of participants will take two years. Based upon the mean number of laparoscopic adnexectomies performed annually at the department of Obstetrics and Gynecology of the participating centre (36) we estimate that the duration of recruitment will be 21 months. Based upon the follow up (6 months) and the period of analysis/reporting (3 months) the total study period will be 2.5 years. First publication will be possible within four years of trial commencement.

Our sample size calculation has allowed for a 15% loss to follow up rate. In order to minimise rates of attrition we will employ a dedicated research secretary to optimize recruitment and follow up.

6.3. Statistical Analysis

We will calculate a 95% confidence interval of the difference in the proportions of women with a successful removal of an adnexal cyst. Non inferiority of the intervention (vNOTES) will be concluded

when 15% lies above the upper limit of this confidence interval. For this primary analysis, adjustments for prognostic factors will not be made in the first instance; the effect of the variables listed in Section 3.5 (Stratification of randomisation) will be explored as a secondary analysis. Continuous measures (VAS scores) will be analysed using analysis of covariance (adjusting for baseline value). Multilevel models for repeated measurements will also be used to compare the mean differences in VAS pain scores between groups overall at all time points, thereby maximising the power of the data available.

Analysis will be performed on an 'intention to treat' basis in the first instance as recommended in the CONSORT statement. A 'per protocol' analysis will also be performed to test the robustness of the results obtained. As a conservative measure, estimates of effect sizes between the two arms will be presented as point estimates with two-sided 95% confidence intervals. The trial can only conclude non-inferiority if 15% lies out of the upper band of the confidence interval (i.e. vNOTES 15% less successful than laparoscopic treatment).

Baseline characteristics of the patients enrolled in the two groups will be compared to ensure that randomisation has produced comparable groups of participants, and will be covariates in the modelling procedure.

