3.2. Determining eligibility

All women regardless of age and parity presenting with a symptomatic or asymptomatic persistent benign adnexal mass on clinical examination who provide consent to participation are eligible in the NOTABLE trial based on the findings of the ultrasound findings and will be randomised before the procedure.

The following inclusion/exclusion criteria will be applied to assess eligibility:

Inclusion criteria:

- All women regardless of age and parity with a symptomatic adnexal mass presumed to be benign based on ultrasound examination by applying the IOTA simple rules
- All women regardless of age and parity with an asymptomatic persistent adnexal mass presumed to be benign based on ultrasound examination by applying the IOTA simple rules

- Written informed consent obtained prior to surgery

Exclusion criteria:

- History of hysterectomy by any technique
- History of rectal surgery
- Suspected rectovaginal endometriosis
- Suspected endometriotic cyst
- Solid adnexal mass
- High suspicion of adnexal malignancy based on clinical, ultrasound or biochemical findings
- History of pelvic inflammatory disease, especially prior tubo-ovarian or pouch of Douglas abscess
- Active lower genital tract infection e.g. Chlamydia, N. gonorrhoeae
- Virginity
- Pregnancy
- Need for other uterine surgical intervention (i.e. endometrial ablation, resection, myomectomy or hysterectomy)
- Additional pathology necessitating hysterectomy
- Failure to provide written informed consent prior to surgery

Obesity (Body Mass Index or BMI > 30), nulliparity or large diameter of the cyst are not considered to be an exclusion criterion per se. We will only stratify for the diameter of the cyst because this parameter was perceived by the gynaecological surgeon as the most important one to influence the difficulty of the procedure. Stratification for three parameters in a small pilot randomised trial with a limited number of participants is not sensible.

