3.5. Stratification of randomisation

A blocked randomisation procedure will be used to avoid chance imbalances for the parameter 'cyst diameter'. We preferred not to use minimisation because this trial was not funded and we therefore could not afford to buy licenses for a computer-based algorithm for minimisation. Although parity and BMI may be prognostic parameters influencing the chances of the successful removal of the adnexal mass, we preferred to limit the stratification to one parameter for reasons of simplicity based on what is affordable to conduct the present research. It was not considered appropriate to use three strata in a small pilot study including a small number of participants.

To avoid any possibility of foreknowledge, the randomised allocation will not be given until all eligibility and stratification data have been given.

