5.2. Primary clinical outcome measure

The proportion of women successfully treated by removing the adnexal mass without spill, using a dichotomous outcome measure, will be used as a measure of efficacy. An important consideration in adnexal mass surgery is the inadvertent opening of the ovarian capsule. The likelihood of cyst rupture during removal by laparotomy or laparoscopy ranges from 10.5% to 41.8% in published studies (15). We will consider any spontaneous rupture of the cyst or any need to aspirate the cyst to allow removal from the abdominal cavity as treatment failures, even if the content of the ruptured cyst does not spill freely inside the cavity but remains within the endobag. By avoiding any subjective interpretations this rigorous definition allows an objective measure of success. As the risk of rupture may be associated to the cyst size, due to the stratified random sequence generation we anticipate that the risk of rupture due to the cyst size rather than the technique used will be symmetrically applicable.

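### The primary non-inferiority interval ignores cyst diameter, the only stratification factor, and is therefore wider than necessary if diameter predicts failure, although no planned power is lost

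*Protocol*

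**What the plan says.** Section 3.5 explains the stratified allocation: "A blocked randomisation procedure will be used to avoid chance imbalances for the parameter" of cyst diameter. Parity and BMI are named there as possibly prognostic but are left out for simplicity. Section 3.2 gives the reason for choosing diameter: "this parameter was perceived by the gynaecological surgeon as the most important one to influence the difficulty of the procedure". Section 5.2 ties it to the primary outcome ("As the risk of rupture may be associated to the cyst size") and relies on the stratified allocation to balance that risk.

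Section 6.3 then sets the primary analysis: "For this primary analysis, adjustments for prognostic factors will not be made in the first instance". The effect of the section 3.5 variables is left to a secondary analysis. The same section says that baseline characteristics will enter a modelling procedure as covariates, without naming the model. Results are to be given so that "estimates of effect sizes between the two arms will be presented as point estimates with two-sided 95% confidence intervals", and non-inferiority is concluded if the upper limit is below 15 percentage points.

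On the strata themselves, section 6.1 refers to three strata for the randomisation, whereas section 3.5 says three strata were not thought appropriate.

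**The concern.** The analysis does not follow the design. Stratified allocation balances the arms on diameter, so the treatment difference varies less from trial to trial than an unadjusted SE assumes, provided that diameter is prognostic. The unadjusted SE keeps that between-stratum variance.

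The conclusion turns on one confidence limit against one margin in 66 women. Unneeded width can only make non-inferiority harder to show. This is a choice written into 6.3, not a detail left open.

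**Working it through.** **Inputs.** Section 6.1 gives a one-sided test ("We calculated the sample size with a one-sided test for non-inferiority studies for the primary outcome"), the power and rates ("To achieve 80% power to demonstrate non-inferiority under the assumption of similar success rates of 95% in both groups"), the 15-point margin ("even if 15% less women had successful removal of a benign adnexal mass by using the vNOTES approach"), 27 per group, 32 after 15% drop-out, and 66 women finally. Success or failure rates by diameter stratum are not given anywhere. Those below are assumptions, with three equal strata and equal rates in both arms.

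**Step 1: the plan's own figure.** n per arm = 2p(1−p)(z₁₋α + z₀.₈₀)²/δ² = 2 × 0.95 × 0.05 × (1.645 + 0.842)²/0.15² = 26.1, so 27 per arm and 54 in total. Dividing by 0.85 gives 31.8, so 32 per arm and 64 in total. Both match 6.1, at one-sided α = 0.05. The variance used is p(1−p) with no term removed for strata, so the trial was sized on the unadjusted comparison.

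**Step 2: what stratifying removes.** With stratum failure rates p_s and mean p̄, the SE ratio (stratified to unadjusted) is √{mean[p_s(1−p_s)] / [p̄(1−p̄)]}. For failures of 1/5/9%: mean[p_s(1−p_s)] = (0.0099 + 0.0475 + 0.0819)/3 = 0.0464; p̄(1−p̄) = 0.0475; ratio = 0.989.

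At the planned 5% mean failure with 27 per arm, the unadjusted two-sided 95% half-width is 1.96 × √(2 × 0.0475/27) = 11.63 points.

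| Failure by stratum | Stratified half-width | SE reduction |
|---|---|---|
| 5/5/5% | 11.63 | 0% |
| 2/5/8% | 11.55 | 0.6% |
| 1/5/9% | 11.49 | 1.1% |
| 0/5/10% | 11.42 | 1.8% |
| 0/0/15% (extreme) | 11.00 | 5.4% |

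If failures are more frequent and size-driven:

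| Failure by stratum | Mean | p̄(1−p̄) | Mean p_s(1−p_s) | SE reduction |
|---|---|---|---|---|
| 2/5/20% | 9% | 0.0819 | 0.0757 | 4% |
| 2/15/40% | 19% | 0.1539 | 0.1290 | 8% |
| 2/10/60% (extreme) | 24% | 0.1824 | 0.1165 | 20% |

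**Step 3: is the second table possible under this protocol?** Section 5.2 counts any aspiration needed for removal as failure, even when the contents stay in the bag. Section 4.1.1 describes large adnexa being bagged and their contents aspirated. Section 4.1.2 provides for aspiration when the bag cannot be drawn out intact. Large cysts could therefore become failures by definition. The protocol gives no figure for how often.

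**Step 4: effect on the conclusion.** Simulation with 33 per arm (11 per arm per stratum), no true difference, and non-inferiority declared when the two-sided 95% upper limit is below 15 points:

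| Failure by stratum | Unadjusted Wald | Mantel-Haenszel, Sato variance |
|---|---|---|
| 1/5/9% | 80.9% | 81.3% |
| 2/5/20% | 59.2% | 62.4% |
| 2/15/40% | 35.8% | 41.4% |
| 2/10/60% | 26.5% | 45.4% |

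The simulated one-sided error, nominally 0.025, is about 0.03-0.04 for the stratified analysis and 0.01-0.04 for the unadjusted one.

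**The case against.** An unadjusted primary analysis with an adjusted secondary one is stated in advance and is defensible in a small pilot with few failures. At the planned success rate the expected number of failures is 27 × 0.05 = 1.35 per arm, and the gain from stratifying is about 1% in SE. This stands, and it limits the point to an efficiency improvement.

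Not every stratified method helps. At 27 per arm with 99/95/91% success, a simple stratified Wald interval had a mean SE of 0.0520 against a true SD of 0.0587, and the chance of concluding non-inferiority was 70.6% either way. At 33 per arm, a stratified Miettinen-Nurminen score interval with its small-sample factor lowered that chance from about 59% to 55%. This also stands, and it decides which method to recommend.

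A reader might infer three stronger things that the protocol does not support:

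- That the trial gives up power it counted on. Step 1 shows that the sample size took no credit for stratification.
- That the 10.5% to 41.8% rupture range in 5.2 and 6.1 shows how failure varies with cyst size. It is a range across published studies, not across diameters.
- That diameter is an established main driver of rupture. Section 3.2 reports a surgeon's perception of difficulty, 5.2 says only that an association may exist, and 3.5 allows that parity and BMI may matter too.

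**Conclusion.** The point holds as a modest one. The primary interval leaves out the only stratification factor and is wider than necessary if diameter predicts failure. If diameter is not prognostic, nothing is lost.

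With three equal strata, the SE reduction is about 0-2% at 95% success, about 4-8% with more frequent, size-driven failures, and 20% in the extreme case. All these figures rest on assumed stratum rates.

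Conservative here describes only the effect of ignoring the strata. It does not mean that the unadjusted Wald interval holds its nominal error with so few failures, since its simulated error reached about 0.04. Nor should a reader infer that omitting diameter raises the risk of a false non-inferiority claim through the SE, because ignoring a prognostic stratifier works the other way.

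A larger influence on the chance of success is a separate matter: 6.1 reproduces at one-sided 0.05, while the decision uses a two-sided 95% interval. On that rule, power at 27 per arm is 71.5%.

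**What to change.** First reconcile the number of diameter strata. Section 6.1 uses three, while 3.5 says three were not appropriate. Section 3.5 may mean three factors, as 3.2 does when it rejects stratifying on three parameters. The strata actually used in the allocation list should be stated.

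Then amend 6.3 so that the primary estimate is the Mantel-Haenszel risk difference stratified by those cyst-diameter strata, with a sparse-data variance (for example Sato's), and the unadjusted difference is reported as a sensitivity analysis.

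The cost is a sentence in 6.3 and a correction in 3.5 or 6.1, with no new data. The downside is small: with few failures per stratum the stratified interval can be slightly anti-conservative (the 0.03-0.04 above), and the gain is negligible if 95% success holds. If the unadjusted analysis is kept as primary, 6.3 should say why.
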